4.2 General Concomitant Medication and Supportive Care Guidelines

- 4.2.1 Supportive care measures will be consistent with standard practice of the Stanford BMT Program. Standard care measures are included by not limited to measures for skin care, mucositis, nausea, diarrhea, constipation, pain control, infection prevention and patient and family education.
- 4.2.2 Transfusion support for red blood cells and platelets will be consistent with standard practice of the Stanford BMT Program.

4.3 Duration of Therapy

- 4.3.1 See table below for time lines.

Non-Myeloablative Allogeneic Transplant

Day - 11	Day - 10	Day - 9	Day - 8	Day - 7
----------	----------	---------	---------	---------

TLI ATG	TLI ATG	TLI ATG	TLI ATG	TLI ATG
Day - 4	Day - 3	Day - 2	Day - 1	Day 0
TLI	TLI Begin Tacrolimus	TLI	TLI x 2	Allogeneic Transplant

4.3.2 Active treatment continues post-allogeneic transplant for approximately 3 – 4 months and then care is transitioned back to the BMT clinic for ongoing monitoring and care.

4.4 Duration of Follow Up

Patients will be followed for 2 years after transplant. Subsequent follow-up will be consistent with standard practice of the Stanford BMT program.

4.5 Criteria for Removal from Study

4.5.1 Patients who develop severe adverse reaction to ATG infusion, such as serum sickness that result end-organ damage will be removed from study.

4.6 Alternatives

4.6.1 Alternatives may include continued standard therapies, other investigational therapies or no therapy.

4.7 Compensation

Subjects will not be paid for their participation in the study.

5. INVESTIGATIONAL AGENT/DEVICE/PROCEDURE INFORMATION

5.1 Investigational Agent/Device/Procedure

5.1.1 Non-myeloablative allogeneic transplant using total lymphoid irradiation (TLI) and anti-thymocyte globulin (ATG):

As discussed earlier, using a non-myeloablative preparation regimen for allogeneic transplant preserves the benefit of graft versus tumor effect but decreases the toxicity. However, one major complication found in our previous approach using TBI/fludarabine regimen is GVHD. Recently, Lowsky et al. (32) have extended the preclinical model of Strober and colleagues to the clinic using a novel conditioning strategy of total lymphoid irradiation (TLI) and anti-thymocyte globulin (ATG) prior to allogeneic HCT. In this recent report, the incidence of acute GVHD was just 5%, prompt multi-lineage engraftment was demonstrated, and promising efficacy was reported in hematologic malignancies, including mantle cell lymphoma and DLBCL(32). Since this report, we have performed allogeneic transplant with both related and unrelated donors using TLI/ATG in over 150 patients who have a variety of hematological malignancies including mantle cell lymphoma, transformed lymphoma, follicular lymphoma, chronic lymphocytic leukemia, acute myeloblastic leukemia, myelodysplastic syndrome and myelofibrosis. The overall experience has re-demonstrated the low incidence of acute GVHD and preserved graft versus tumor effect.

5.2 Availability

All agents used in this study are commercially available. Total lymphoid irradiation is part of standard care provided by Stanford Radiation Oncology department.

5.3 Agent Ordering

All agents used in this study are commercially available and will be ordered accordingly.

5.4 Agent Accountability

The agents will be kept and monitored by Stanford central pharmacy.

6. DOSING DELAYS/DOSE MODIFICATIONS

No dose modifications will be made.

7. ADVERSE EVENTS AND REPORTING PROCEDURES

7.1 Potential Adverse Events

Tacrolimus

- Human Toxicology: Nephrotoxicity is the most frequent side effect of tacrolimus. Other frequently observed side effects include hypertension, hirsutism, tremors, paresthesias, hepatotoxicity, hypomagnesemia, and hyperkalemia. Transient gastrointestinal symptoms have also occurred, to include anorexia, nausea and ileus. The drug has demonstrated a relative lack of myelotoxicity.
- Pharmaceutical Data Formulation: Tacrolimus is available for oral and intravenous administration. The intravenous solution is available as 1 ml ampules containing 5 mg/ml. Tacrolimus should be administered intravenously over 2-6 hours. Longer infusion times are acceptable and sometimes better tolerated. The contents of the ampules should be diluted 0.9% NaCl injection or 5% dextrose injection
- Supplier: This drug is commercially available.

Mycophenolate Mofetil

- Human Toxicology: The principal side effects include diarrhea, leukopenia, vomiting and infection. The drug is also associated with abdominal pain, nausea, hypertension and anemia.
- Pharmaceutical Data: Mycophenolate Mofetil is available in 250 mg capsules and 500 mg tablets. Mycophenolate Mofetil should be taken on an empty stomach.
- Supplier: Mycophenolate Mofetil is commercially available.

Granulocyte-Colony Stimulating Factor

- Human Toxicology: The primary side effect of G-CSF is bone pain and is more common with higher doses of G-CSF.
- Pharmaceutical Data: G-CSF is available in vials containing 300 μ g or 480 μ g at a concentration of 300 μ g/ml. G-CSF should be refrigerated. G-CSF is given as a daily subcutaneous injection.
- Supplier: G-CSF is commercially available.

Anti-thymocyte Globulin (ATG)

- Thymoglobulin® is a rabbit-thymocyte globulin. It is the purified, sterile, IgG fraction of immune serum of rabbits immunized with human thymus lymphocytes. ATG is a lymphocyte-selective immunosuppressant. It is believed to act by modifying the number and function of lymphocytes.
- Administration: Thymoglobulin® is diluted in 0.9% NaCl. Thymoglobulin® is given intravenously as a 4-

6 hour infusion into a central vein.

- Potential Toxicities: Thymoglobulin® may cause:
Cytopenia of any cell line
Pyrogenic action (ATG causes chills and fever in a high proportion of patients treated)
Fluid retention
Allergic reactions (rash, pruritus, urticaria, wheal and flare reactions are reported, as well as bronchospasm and anaphylactic shock)
A serum sickness-like syndrome may develop. This is best prevented by steroid co-administration.
EBV lymphoproliferative disorders have been associated with administration of anti-thymocyte globulin in highly immunosuppressed patients.
- Because of the potential for anaphylaxis, resuscitation equipment should be available during administration. After an anaphylactic reaction, infusion should not be resumed. A central line should be established and oxygen, as well as resuscitation equipment should be available.

Total Lymphoid Irradiation (TLI)

- TLI may cause nausea, vomiting, diarrhea, temporary hair loss and painful swelling of the salivary glands for a few days. The TLI in this protocol is approximately one-fifth of that used in standard NHL treatments. Therefore, these side effects most likely will be milder and severe acute side effects are not expected. The risk of secondary malignancies after the low dose TLI is yet to be determined.

Total Skin Electron Beam Therapy (TSEBT)

Acute side effects can include a skin burn that is much like a moderate to severe sun burn (worse in patients who burn but do not tan when exposed to sun), deep tanning (in those who tan after sun exposure), itching and fatigue. Although these acute side effects are occasionally severe, they are self-limited if appropriate supportive therapy is administered in a timely fashion.

Long-term side effects can include generalized dry skin and permanently decreased secretion of sweat and oil on much but not all of the skin, scattered dilated blood vessels (telangiectasias), pigmentation changes, and partial or complete scalp hair loss which is more severe in males with signs of thinning hair than in females.

Extracorporeal photopheresis (ECP)

ECP is a very well-tolerated procedure. Transient hypotension may occur in some patients during the collection phase of the treatment, but this is asymptomatic. Some patients may experience low-grade fevers a few hours after ECP.

Some patients with CTCL may experience an increase in pruritus or redness during the course of ECP.

In all of the various patient groups treated, no immunosuppression, opportunistic infections, or neoplasia has been associated with ECP. The risk of secondary malignancies after the low dose TLI is yet to be determined.

Finally, although patients with hypertriglyceridemia do not experience further adverse events during ECP, they may have a less efficacious treatment because of the inability of the UVAR machine to separate the WBCs from the lipid-rich blood. Because of this, patients should have triglyceride levels of less than 300 mg/dL and should eat a very low fat or non-fat diet starting the evening before the procedure.

7.2 Adverse Event Reporting

Appendix C outlines AE and SAE reporting Guidelines.

8. CORRELATIVE/SPECIAL STUDIES

8.1 Laboratory Correlative Studies

8.1.1 Donor Cell Chimerism

8.1.1.1 Collection of Specimens

Peripheral blood will be drawn on day +28, +56, +90, and +180.

Bone marrow biopsy will be performed on day +90.

8.1.1.2 Handling and Shipping of Specimens

Per standard BMT guidelines.

8.1.1.3 Site(s) Performing Correlative Study

Stanford HLA Typing Laboratory will be responsible for performing the donor chimerism study.

8.1.1.4 Coding of specimens for privacy protection

Specimens will be coded for privacy protection.

8.1.2 Profile of Grafting Immune Cells

8.1.2.1 Collection of Specimens

Peripheral blood will be drawn before preparative regimen and on day +30, +60, +90, and +180 post transplant.

8.1.2.2 Handling and Shipping of Specimens

Per standard BMT guidelines.

8.1.2.3 Site(s) Performing Correlative Study

Study of T cell cytokine and chemokine receptor profile will be performed in the Stanford Cellular Therapy Facility (CTF).

8.1.2.4 Coding of specimens for privacy protection

Specimens will be coded for privacy protection.

8.1.3 Donor T Cell Trafficking

8.1.3.1 Collection of Specimens

Two 5 mm punch skin biopsy of target lesions will be performed in Stanford Cutaneous Lymphoma Center on day +90 and at the time of tumor regression/progression.

8.1.3.2 Handling and Shipping of Specimens

Per standard BMT guidelines.

8.1.3.3 Site(s) Performing Correlative Study

Stanford Cellular Therapy Facility (CTF)

8.1.3.4 Coding of specimens for privacy protection

Specimens will be coded for privacy protection.

8.1.4 Regulatory T Cell (Treg)

8.1.4.1 Collection of Specimens

Peripheral blood will be drawn on day +30, +60, +90, and +120 post transplant.

8.1.4.2 Handling and Shipping of Specimens

Per standard BMT guidelines.

8.1.4.3 Site(s) Performing Correlative Study

Study of Treg will be performed in the Cellular Therapy Facility (CTF).

8.1.4.4 Coding of specimens for privacy protection

Specimens will be coded for privacy protection.

8.1.5 Tumor Immune Response

8.1.5.1 Collection of Specimens

Peripheral blood will be drawn on day +60, +90, and +180.

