4.1.2 Allogeneic Transplant: Preparative Regimen

- d) Total Lymphoid Irradiation (TLI) Administration: TLI is administered ten times in 80c- 120c Gy fractions on day -11 through day -7 and day -4 through day -1 according to the above delineated schedule. TLI is administered from a 6 MeV linear accelerator (photon beam). The radiation field (four fields—two anterior and two posterior) will include all major lymphoid organs including the thymus, spleen and lymph nodes. A radiation oncologist will evaluate patients prior to conditioning to determine blocks and radiation ports. TLI will generally be administered between 10 a.m. and 1 p.m. Since TLI can cause nausea, premedication with antiemetic therapy is needed. TLI schedule may be adjusted based on schedule of radiation therapy department.
- e) Anti-thymocyte Globulin (ATG) Administration: ATG will be administered five times intravenously at 1.5 mg/kg/day from day -11 through day -7 for a total dose of 7.5 mg/kg. ATG doses will be based on the adjusted ideal body weight. Premedication for ATG will include benadryl 25-50 mg, Tylenol 650 mg and solumedrol 1.0 mg/kg.
- f) Total skin electron beam therapy (TSEBT) Administration: TSEBT will be given to patients who have extensive skin involvement such as wide spread plaques, tumors, or erythroderma with significant tumor infiltration, as part of cytoreduction prior to transplant. The length of therapy and dose of TSEBT will be determined by the radiation oncologist and individualized based on the patient's presentation and treatment history. In patients receiving TSEBT, TLI will begin during the last two week of TSEBT.

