8.1.5.3 Site(s) Performing Correlative Study

Stanford Human Immune Monitoring Center (HIMC) Laboratory will be responsible for serum storage. The testing of antibody against patients' tumor cells will be performed by [name] in HIMC laboratory.

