9. STUDY CALENDAR

	BS	Post-Transplant Day							
		±5 days	±5 days	±10 days	± 2 wks	± 2 wks	± 2 wks	± 4 wks	± 4 wks
		d+30	d+60	d+90	d+180	d+270	d+365	d+540	d+730
Informed Consent	X								
Path Review	X								
H&P/KPS	X								
PFT	X								
Echo	X								
CBC with diff	X								
Chemistry: BMT I	X								
HLA confirmed	X								
BMT Panel (serologies)	X								
CXR	X								
EKG	X								
STR subsets: PB		X	X	X	X	X	X**		X
BM bx/asp**	X			X			X		X
Research Samples		X	X	X	X				
Skin Biopsy	X			X					
Flowcytometry** (SS only)		X		X	X	X	X	X	X
Disease Status/Response**	X			X		X	X	X	X
GVHD assessment	X	X	X	X	X	X	X		X

** Per Attending Physician's discretion

Correlative Study Calendar

	Donor Chimerism	Chemokine Receptor Profile	Th1/Th2 Phenotype	Treg Cell Quantity	Treg Cell Function	Skin Biopsy Pathology	Skin Biopsy T Cell Trafficking	Derm Clinical Assessment	Bone Marrow Biopsy	CTL Assay	Tumor Cell Banking
Pre TSEBT		X		X		X		X	X	X	Sezary only
Pre TLI/ATG		X		X		X	First 5 pt	X			
Pre Infusion		X		X							
+ 30 day	X	X	X	X	First 5 pt			X			
+ 60 day	X	X	X	X				X			
+ 90 day	X	X	X	X	First 5 pt	X	First 5 pt	X	X	X	
+ 180 day	X	X	X	X	First 5 pt		First 5 pt	X	X	X	
+ 270 day	X	X	X	X				X			
+ 1 year	X	X	X	X	First 5 pt		First 5 pt	X	X	X	
+ 2 year	X							X	X		
Cell Product		X	X	X							
Pre ECP		X	X	X							
Post ECP		X	X	X							
Disease Regression						X		X			
Disease Progression						X		X			
Sample		Up to 5 GGT			5 mm punch	5 mm punch		Routine	2 GTT for effector	2 GTT	
Site	HLA Lab	HIMC	CTF	CTF	CTF	Path	CTF	Cut Lym Clinic		HIMC	HIMC
Assay	Chimerism: CD3, CD19, CD56, CD15	Skin: CCR4, CCR10, CLA; LN: CCR7	Th1: IL-2, IFN γ ; Th2: IL-4, IL-10	FoxP3 positive	Inhibition of MLR	Monitoring Residual Disease	Lymphocyte Donor Chimerism, Chemokine receptor		FAM-VAD Assay	Use as Target Cell for CTL	

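### The serum antibody sub-study (8.1.5) has no pre-transplant sample, and the correlative calendar schedules a different assay whose baseline and tumour-cell banking are tied to a Pre TSEBT visit

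*Combined protocol and SAP*

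**What the plan says.** Section 8.1.5.1 gives the whole specimen schedule for the tumour immune response study: "Peripheral blood will be drawn on day +60, +90, and +180". Under 8.1.5.3 the HIMC laboratory "will be responsible for serum storage", and the assay is described as "The testing of antibody against patients' tumor cells". Section 8.1.5 does not mention a CTL assay and does not say where the tumour cells for the antibody test come from.

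The Correlative Study Calendar in section 9 has a CTL Assay column and a Tumor Cell Banking column, but none for antibody or serum. The CTL column is marked at Pre TSEBT, +90 day, +180 day and +1 year, and the sample is given as "2 GTT for effector". Banking has one entry, in the Pre TSEBT row, restricted to Sezary patients. The stated purpose of the banked cells is "Use as Target Cell for CTL".

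Two other provisions bear on this. Section 8.1.2.1, on the immune-cell profile, does include a baseline: "Peripheral blood will be drawn before preparative regimen and on day +30, +60, +90, and +180 post transplant". Section 4.1.2(f) makes TSEBT conditional: "TSEBT will be given to patients who have extensive skin involvement".

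**The concern.** A study of antibody against tumour cells around a transplant is most informative when each patient serves as his or her own control. If the first serum is taken at day +60, a positive result then may reflect antibody the patient already had. That sample cannot be recovered once conditioning has begun.

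The second difficulty is that section 8.1.5 and the calendar describe different laboratory studies. Staff following 8.1.5 would store serum at +60, +90 and +180. Staff following the calendar would collect effector cells at Pre TSEBT, +90, +180 and 1 year, and no serum.

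The third is that the CTL baseline and the banking of its target cells are attached to a treatment that only some patients receive. The CTL column carries no Sezary restriction while the banking column does, so the calendar schedules CTL blood in patients for whom it schedules no banked targets.

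At stake is what this sub-study can say about anti-tumour immunity after transplant. That is relevant to the graft-versus-lymphoma objective in section 1.1, but it is not a listed endpoint.

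**Working it through.** The plan gives no sample size, rate or power for this sub-study, so there is no figure to reproduce. The check sets the schedules side by side and counts.

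| Source | Assay or specimen | Before transplant | +60 | +90 | +180 | 1 year |
|---|---|---|---|---|---|---|
| 8.1.5.1 and 8.1.5.3 | serum antibody | none | yes | yes | yes | none |
| Correlative calendar | CTL | Pre TSEBT only | none | yes | yes | yes |
| Correlative calendar | tumour-cell banking | Pre TSEBT, Sezary patients | none | none | none | none |

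1. *Serum baseline.* Pre-transplant draws in 8.1.5.1: 0 of 3. No other section schedules serum for this study, and the Research Samples row of the main calendar is blank at baseline and begins at d+30. With serum at +60, +90 and +180, the contrasts available within a patient are among those three days. A contrast across the transplant is not available.

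2. *CTL baseline.* Pre-transplant CTL time points: 1 of 4. The cellular assay therefore does have a planned baseline, but only in the Pre TSEBT row. The Pre TLI/ATG row, which applies to everyone who starts conditioning, has no CTL mark and no banking mark.

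3. *Agreement between the two schedules.* The days in 8.1.5.1 are {+60, +90, +180}; the CTL times are {Pre TSEBT, +90, +180, 1 year}. They share two: +90 and +180. The +60 draw appears only in 8.1.5.1, and Pre TSEBT and 1 year only in the calendar. The main calendar's Research Samples row ends at d+180, so it does not carry the 1-year CTL draw either.

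4. *Opportunity for a baseline aliquot.* Section 8.1.2.1 already calls for blood before the preparative regimen, and the correlative calendar marks chemokine-receptor and Treg blood at Pre TLI/ATG. The main calendar's blank baseline cell disagrees with both and needs the same correction. Section 4.1.2 lists TSEBT under the preparative-regimen heading but describes it as cytoreduction before transplant. The timing in 8.1.2.1 is therefore itself ambiguous for patients who receive TSEBT.

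5. *How many patients are affected.* Section 3.1.1 admits both MF and Sezary syndrome, up to 40 patients (12.4.1), with no planned split and no expected share receiving TSEBT. No patient count follows from the documents, and none is offered here.

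The Pre TSEBT row has eleven cells matching the eleven column headings, so its CTL and banking entries can be read with confidence. The Sample, Site and Assay rows at the foot of the table appear shifted in the text version. Nothing above depends on the exact alignment of those rows.

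**The case against.** Several points on the other side are sound.

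- **The Pre TSEBT label may simply mean baseline.** That row also holds the only pre-transplant bone marrow biopsy in the correlative calendar, while 4.1.1(a) expects marrow from patients before therapy and the main calendar marks it at baseline without a TSEBT condition. On this reading no patient loses the visit and only the label is wrong. This is plausible and stands. It reduces the problem to a definition that should be written down.
- **Many Sezary patients may receive TSEBT anyway.** Section 2.1 describes Sezary syndrome as erythrodermic, and 4.1.2(f) names erythroderma with significant tumour infiltration among the reasons for TSEBT. The number without the visit could be small.
- **Banking only in Sezary patients may be deliberate.** Circulating tumour cells can be collected from blood in that group. As a feasibility limit this is reasonable; what is missing is a statement of the analysis set it implies.
- **The work is exploratory.** Section 12.3.6 claims no power beyond exploration, and the sub-study feeds neither the endpoints in 12.1 nor the sample size in 12.4.2.

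A reader might go further and infer that new immunity cannot be shown at all. The documents do not support that: the calendar marks a CTL assay before transplant as well as after, so the missing baseline concerns serum. Nor does the protocol say that demonstrating new or graft-derived immunity is the aim; section 2.4 gives no hypothesis for this study. A baseline would not by itself establish graft origin either.

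A reader might also infer that serum from MF patients is untestable. That does not follow. The banked cells are designated for the CTL assay, and the source of targets for the antibody test is not stated. Skin biopsies are taken, although no section says that tumour cells are kept from them.

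None of this supplies a pre-transplant serum sample or reconciles 8.1.5 with the calendar.

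**Conclusion.** The point holds in a limited form. The antibody study has 0 of 3 draws before transplant and can describe change only from day +60 to +180. The correlative calendar omits the antibody assay, schedules a CTL assay that 8.1.5 does not mention, and shares only +90 and +180 with it. The one CTL baseline and the one banking entry sit at a visit that, read literally, does not exist for a patient not given TSEBT; if the label means any pre-therapy baseline, this last part is a matter of wording.

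The conclusion rests on reading 8.1.5.1 as the complete draw schedule for the antibody study and on the Pre TSEBT row as it stands. It does not rest on any assumed MF/Sezary split. The consequence is confined to an exploratory correlative study, so this is a worthwhile improvement and not a flaw in the trial's main inference.

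**What to change.** 1. Add a pre-regimen serum aliquot to 8.1.5.1, taken at the research draw already scheduled in 8.1.2.1, and mark baseline in the Research Samples row of the main calendar.
2. Define the tumour-cell banking and CTL baseline visit as the first research draw before any TSEBT or TLI/ATG, and relabel the calendar row to match. Use the same definition for the baseline in 8.1.2.1.
3. State that the CTL analysis set is patients with banked tumour cells, which under the current calendar means Sezary patients, and state the source of target cells for the antibody test.
4. Make 8.1.5 and both calendars name the same assays on the same days, including whether +60 and 1 year are collected and for which assay.

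The cost is one extra aliquot per patient (an added tube at the same venepuncture if the scheduled tubes do not yield serum) and text edits. The downside is a smaller stated analysis set for the CTL assay. The trial's endpoints, sample size and treatment schedule do not change.

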8.1.5.2 Handling and Shipping of Specimens

Per standard BMT guidelines.

8.1.5.3 Site(s) Performing Correlative Study

Stanford Human Immune Monitoring Center (HIMC) Laboratory will be responsible for serum storage. The testing of antibody against patients' tumor cells will be performed by [name] in HIMC laboratory.

